This application is an investigator-initiated, University-sponsored academic research program. Sinapi Biomedical are sub-contracted to supply the device. Sinapi manufactures a CE marked Ellavi balloon uterine tamponade system (Fig 1). The central tube is very similar to the Levin tube, but without the multiple suction holes, and served as the starting point for development of the U-STAT device.

Methods

This exploratory proof of concept (POC) clinical trial will build on our experience with our initial clinical studies of the improvised STUT device. This initial trial is designed to assess essential safety, performance, feasibility and acceptability and to give an indication of effectiveness and suitability for a substantive randomized effectiveness trial. It will include a limited number of participants (intervention arm n=40, control arm n=40).

Study type: Investigator-initiated, academic, non-commercial study.

Study Sponsor. Wits Health Consortium, a subsidiary of University of the

Witwatersrand

Study Design: Prospective intervention study

Study Sites: Frere/Cecilia Makiwane hospitals, South Africa

Study Duration: Four months

Study Population: Women 18 years old or more with risk factor(s) for PPH, for planned vaginal or caesarean birth; no serious medical conditions.

Inclusion Criteria

- Age 18 years and older
- Planned vaginal or caesarean birth
- One or more risk factors for PPH. These include
 - o Previous PPH
 - o Hypertension and pre-eclampsia
 - o Induction of labour
 - o Emergency caesarean birth
 - O Anaemia
 - Multiple pregnancy
 - Polyhdramnios
 - Macrosomia
 - Antepartum haemorrhage
- No serious medical conditions
- Provision of signed written informed consent

Intervention: Suction Tube Uterine Tamponade (STUT) using the purpose-designed soft plastic suction catheter inserted after vaginal birth or during caesarean birth. Low-pressure suction applied (approx. 100mmHg). Suction stopped after 30 minutes. If no further bleeding, tube removed. If bleeding resumes, suction continued. If bleeding not controlled within 20 min (or sooner if clinically indicated), proceed to further management according to local standard of care protocols (these might include additional uterotonics, tranexamic acid, compression methods, uterine balloon tamponade or laparotomy).

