Control: This is a pilot proof of concept study with sample size insufficient for a formal randomized comparison. In order to have a valid comparator, participants will be randomly allocated to an intervention and control group (approx. 40 per group). No p values will be calculated. Comparisons will be as risk ratios or mean differences with 95% confidence intervals.

Outcomes

Baseline demography and clinical data will be recorded.

Primary: The primary outcome is the combined frequency of adverse device effects and device deficiencies up to discharge from hospital.

Adverse device effects (ADEs) encompass any adverse event with a reasonable causal relationship resulting from insufficient or inadequate instructions for use; problems with the deployment, implantation, installation, or operation of the device; malfunction of the device; or user error or intentional misuse of the device. They will include device deficiencies such as device expulsion / falling out of the uterus, failed maintenance of suction pressure and tube blockage.

A Serious Adverse Device Effect (SADE) is an adverse device effect that has resulted in any of the consequences characteristic of a serious adverse event. An example of this would be the need for further intervention to treat trauma caused by the device (e.g. sutures, laparotomy, etc).

Secondary efficacy outcomes will include:

- 1. Measured blood loss within 30 minutes after insertion (ml)
- 2. Blood loss >500ml
- 3. Blood loss >1000ml
- 4. Efficiency of suction (assessed through ultrasound assessment of residual blood in the uterus at 30 minutes or blood expressed from the uterus after tube removal)
- 5. Blood pressure, pulse and shock index 15 minutes after vaginal birth or caesarean
- 6. Change in routinely collected haemoglobin levels pre delivery to post delivery
- 7. Blood transfusion
- 8. ICU admission
- 9. Death
- 10. Functionality and acceptability:
 - a. Active bleeding from the uterus continuing for more than 10 minutes (main efficacy outcome).
 - b. Any adverse event
 - c. Pain experienced (No pain/Mild /Severe/Unbearable)
 - d. Need for Additional interventions to stop bleeding (e.g. more uterotonics, compressive measures, UBT, laparotomy, hysterectomy)
 - e. Was STUT effectively inserted? (Yes/No/Unknown)
 - f. How easy was it for health care providers to insert the Suction Tube Uterine Tamponade (easy/moderately difficult/Difficult/failed)

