- g. Did the suction tube remain in place in the uterus until removal (Yes/No/Unknown)
- h. Did the suction tube establish a good seal (no loss of suction) (Yes/No/Unknown)
- Did the suction tube interfere with or facilitate examination for and management of lower genital tract bleeding after vaginal birth (Facilitated/Interfered/Neither/not applicable/Unknown)
- j. Did the suction tube interfere with or facilitate surgical exposure during caesarean birth (Facilitated/Interfered/Neither/Unknown)
- k. Was there any blockage of the suction tube (Yes/No/Unknown)

Recruitment and consent

We plan to approach women at increased risk of PPH awaiting caesarean or induction of labour, pre-labour or in early labour and provide written and/or video information to them. They will be given time to discuss participation with friends and family and then invited to provide signed consent. Consent will be confirmed verbally immediately after birth, prior to device insertion.

Sample size

We aim to use the U-STAT in 40 participants, with a minimum of 25% being vaginal births and 25% caesarean section. 35 participants will provide 90% confidence that the true rate of adverse device effects and device deficiencies is under 10% (+/-10%). The sample is increased to 40 to account for any unexpected procedural difficulties in the first 5 recruits.

Procedures

Participating sites will be supplied with a 'PPH emergency trolley' containing all the supplies needed for STUT and emergency treatment of PPH, as well as forms for screening, enrolment, randomization and data collection. After vaginal birth, the suction tube will be inserted under sterile conditions transvaginally into the uterine cavity. Suction will be applied either with the manual suction device or with a surgical suction unit, set at 100mmHg suction pressure. If there is excessive bleeding which is not controlled by the STUT, the suction tube will be removed and management continued according to local protocols. If effective, the STUT suction will be interrupted every 30 minutes, and removed as soon as bleeding is controlled without suction. All other care will follow local practice. Blood loss will be measured from enrolment until bleeding is controlled (minimum 30 minutes), using a blood collection drape or Maternawell tray, plus blood collected in the UVT suction bottle, surgical suction and swabs.

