19. Tamponade device inserted? 2=Other tube*; 3=Ellavi; 4 = Other	· ·				
20. Time device inserted:		:			

21. Ease of insertion? 1=easy, 2=mod.diff, 3=difficult		
22. Device stable in uterus? 0=No; 1=Yes		
23. Tube air leak? 0=No; 1=Yes; 3=No tube		
25. Effect of device on exam/mx? 1. Facilitated, 2. Interfered, 3.Neither		
26. Exam obscured by blood from ut: 0=No; 1=Yes		
27. Time bleeding stopped.	:	
28. Time vital signs check (+ 15min)	:	
29. Syst BP mmHg		
30. Diast BP mmHg		
31. Pulse /m		
32. Additional oxytocin 0 = No 1= Yes		
33. Additional erg-/syntomentrine 0 = No 1= Yes		
34. Additional misoprostol 0 = No 1= Yes		
35. Additional tranexamic acid 0 = No 1= Yes		
36. Time blood collection measured (>30 min)	:	
37. Blood volume excluding suction jar (ml)		
38. Blood volume in suction jar (ml)		
39. Blood expelled ex ut. after removal of device or after 30 min in control group (ml)		
40. If bleeding persists, measured blood loss post 30min		
41. Laparotomy 0 = No 1= Yes		
42. Compression sutures 0 = No 1= Yes		
43. Uterine devascularization 0 = No 1= Yes		
44. Hysterectomy 0 = No 1= Yes		
45. Other procedure 0 = No 1= Yes*		
46.ICU admission 0 = No 1= Yes		
47. Organ failure 0 = No 1= Yes*		

48. Death 0 = No 1= Yes		
49. Blood transfusion (number of units RBCs)		
50. First Haemoglobin after bleeding controlled (g/dL)		
51. Highest temperature (deg C)		
52. Endometritis 0 = No 1= Yes 9=Unknown		
53. Other complications 0 = No 1= Yes* 9=Unknown		
53. Date of Discharge (DD/MMM/YY)	/ /	

Completed by (initials) :	Date completed	(dd/mmm/yy)
Completed by (initials) .	Date completed	(dd/IIIIIII/yy

Vaginal birth Clinical checklist (remains in hospital records)

Equity for Suction Tamponade Access to treat postpartum haemorrhage: The ESTA project

	1.	○ Consent signed
	2.	Confirm with Mother that still happy with consent
	3.	Ostudy trolley is available with register, U-STAT suction tubes, working suction
	4.	Clean drape or Maternawell tray available
	5.	\bigcirc Manual suction device ready with vacuum pumped or suction machine pressure set to 100mmHg – block tubing to check
	6.	After baby born position drape/Maternawell tray below the buttocks
Aft	er p	lacenta delivered completely:
	7.	Examine vaginally to exclude major lower genital tract trauma
	8.	O Note the time, 24 hr: H H : M M
	9.	○ Open next numbered envelope and note allocation: ○ STUT* ○ Control
	10.	*Insert U-STAT tube to fundus of uterus and start suction

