	11.	\bigcirc *Insertion of tube; \bigcirc easy, \bigcirc moderately difficult, \bigcirc difficult, \bigcirc Failed, \bigcirc not done
	12.	Alternative Management
	13.	*Time tube insertion procedure completed 24 hr: H H : M M
	14.	*Check tube/balloon stable in uterus Yes / No / Onot used
	15.	Ocontinue routine care including repair of bleeding tears
	16.	*Effect of device on exam/mx of lower genital tract bleeding? Facilitated; Interfered; Neither; Unknown
	17.	○ Note the time per vaginal bleeding stopped. 24 hr: H H : M M
	18.	○ 15 minutes after insertion (10 above) note time 24 hr: H H : M M
		Systolic BP Diastolic Pulse
	19.	○ 30 minutes after insertion, note time. 24 hr: H H : M M
	20.	
		ml ml
	21.	Replace empty tray, expel blood from the uterus by fundal massage (into tray)
	22.	○ Measure blood loss in tray = RESIDUAL
		ml ml
	23.	*disconnect suction. If no bleeding in 10 minutes, remove U=STAT tube
	2/	*If bleeding continues replace empty tray continue suction plus other measure

25. When bleeding stopped, measure blood loss in tray = Secondary blood loss
ml ml
26. *Measure blood loss in suction bottle
ml ml
27.
○ None
The participants will be followed till discharge and the outcome data, as well as any complications, recorded.

Caesarean birth Clinical checklist (remains in hospital records)

Equity for Suction Tamponade Access to treat postpartum haemorrhage: The ESTA project

	1.	○ Consent signed
	2.	Oconfirm with Mother that still happy with consent
	3.	OStudy trolley is available with register, U-STAT suction tubes, working suction
	4.	Clean drape or Maternawell tray available for post-op use
	5.	○ Manual suction device ready with vacuum pumped or suction machine pressure set to 100mmHg – block tubing to check
	6.	\bigcirc After birth of baby, open next numbered envelope and note allocation: \bigcirc STUT* \bigcirc Control
Aft	er p	placenta delivered completely:
	7.	○ Note the time, 24 hr: H H : M M
	8.	\bigcirc *Insert U-STAT tube to fundus of uterus and lower end through cervix and vagina, ask assistant to connect and start suction
	9.	\bigcirc *Insertion of tube; \bigcirc easy, \bigcirc moderately difficult, \bigcirc difficult, \bigcirc Failed, \bigcirc not done
	10.	. Alternative Management
	11.	. *Time tube insertion procedure completed 24 hr: H H : M M
	12.	. Continue uterine closure
	13.	*Effect of device on visualisation for uterine closure? \(\text{Facilitated}; \text{Interfered}; \) Neither; \(\text{Unknown}\)

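### Blood-loss volume is followed only until bleeding is controlled, which also triggers tube removal, so bleeding that starts later enters no volume and the 500 ml and 1000 ml outcomes have no fixed window

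*Protocol*

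**What the plan says.** The protocol fixes the blood-loss period in several places.

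- **Procedures**, both arms: "Blood loss will be measured from enrolment until bleeding is controlled (minimum 30 minutes". Drape or tray, suction bottle, surgical suction and swabs all count towards the total. The same paragraph says effective suction is to be "interrupted every 30 minutes, and removed as soon as bleeding is controlled without suction".
- **Methods, Intervention**: "Suction stopped after 30 minutes. If no further bleeding, tube removed. If bleeding resumes, suction continued".
- **Outcomes**, secondary 1: "Measured blood loss within 30 minutes after insertion (ml". Secondary 2 and 3 are thresholds given without a time; the third reads only "Blood loss >1000ml".
- **Vaginal birth checklist**, item 23: "disconnect suction. If no bleeding in 10 minutes, remove U=STAT tube". Caesarean checklist item 24 has the same 10-minute suction-off check.
- **Clinical Record Form (CRF)**: "40. If bleeding persists, measured blood loss post 30min". Item 39 takes blood expelled from the uterus after device removal, or after 30 minutes in controls.

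**The concern.** Suction tamponade is a temporary mechanical treatment. One way it can fail is that bleeding returns once the tube is out. The plan's volume measurement ends at about that moment, and the end point is an event after allocation that the device may itself influence.

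Two consequences follow. First, outcomes 2 and 3 are counted over a length of time that differs from woman to woman and depends on how she bled. Second, the period in which a delayed failure would show is not measured in either arm.

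The Methods section says the trial should indicate effectiveness and suitability for a larger randomised trial, and it reports risk ratios and mean differences with 95% confidence intervals. A blood-loss contrast limited to the time on or just after suction is weak support for that decision.

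**Working it through.** The plan gives no figure to reproduce. The check is a comparison of passages, followed by an illustration on assumed inputs.

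**1. Order of steps on the two checklists**

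| Step | Vaginal birth | Caesarean birth |
|---|---|---|
| 30-minute point and residual blood | items 19–22 | items 21–23 |
| Suction disconnected, 10-minute check | item 23 (device arm) | item 24 (device arm) |
| Fresh tray if bleeding goes on | item 24 | none |
| Later tray volume (secondary loss) | item 25 | none |
| Suction bottle | item 26 (device arm) | item 25 (device arm) |

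- The 30-minute and residual readings come before disconnection on both forms, so outcome 1 is an on-suction measure in the device arm.
- An uncomplicated device-arm woman is off suction for about 10 minutes, and her tube is out at about 30 + 10 = 40 minutes. After that neither checklist has a line for a new bleed.
- The bottle reading cannot include vaginal loss while the tube is disconnected or after it is out.
- CRF item 40 applies to both modes of birth but depends on bleeding persisting. A woman who was dry at the check and bled later does not clearly qualify. Item 39 is a single expression of blood, not a period of observation.
- At caesarean, every line after the residual reading is marked device-only. A control who is still bleeding has no later volume line on that form, although Procedures require measurement until control.

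**2. Effect on the mean difference**

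Let r be the proportion bleeding after measurement ends and v the volume each loses. The true device-minus-control difference exceeds the recorded one by r(device) × v(device) − r(control) × v(control).

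Inputs: 40 per arm (Methods). SD 496 ml (Background, a cited caesarean figure, assumed here for both arms and both modes).

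- Half-width of the 95% interval: 1.96 × 496 × √(2/40) = 217 ml.
- Assumed, with r(control) = 0:
  - 0.025 × 200 = 5 ml (2% of the half-width)
  - 0.10 × 500 = 50 ml (23%)
  - 0.20 × 1000 = 200 ml (92%)
- If r and v are equal in the two arms the shift is zero. If late loss is greater in controls the sign reverses.

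**3. Effect on a threshold risk ratio (assumed counts)**

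SE(ln RR) = √(1/a + 1/b − 2/40), where a and b are the device and control counts.

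- Recorded, 4/40 v 8/40: RR 0.50; SE √(1/4 + 1/8 − 2/40) = 0.570; 95% CI 0.16 to 1.53.
- Three late events in the device arm only, 7/40 v 8/40: RR 0.88; SE √(1/7 + 1/8 − 2/40) = 0.467; CI 0.35 to 2.18.
- Three in each arm, 7/40 v 11/40: RR 0.64; SE √(1/7 + 1/11 − 2/40) = 0.429; CI 0.27 to 1.47.
- Three in controls only, 4/40 v 11/40: RR 0.36; SE √(1/4 + 1/11 − 2/40) = 0.539; CI 0.13 to 1.05.

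The same recorded result is compatible with all of these, and the planned data cannot distinguish them.

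**The case against.** A reader might infer that all bleeding after suction stops is lost. The documents do not support that. Stopping suction and removing the tube are separate steps with 10 minutes between them, and bleeding that returns in that interval leads to renewed suction. At vaginal birth it also leads to a fresh tray and a secondary-loss reading. CRF item 40 is there to receive later loss.

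A reader might also infer that the device will look better than it is. That is not shown either. The stopping rule and the 30-minute floor apply to both arms. Because of the floor, a device that brought control forward from, say, 20 to 10 minutes would not shorten the window. The suction-off check and the later bottle reading are device-arm steps, so an uncomplicated device-arm woman may be watched slightly longer than an uncomplicated control. Bias in the device's favour needs more bleeding after removal in that arm. The documents give no rate, and the ethics section reports no complications of the procedure to date.

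The stakes are also limited. The primary outcome is device effects and deficiencies to discharge, the main efficacy outcome is active bleeding beyond 10 minutes, and no p values are planned. Haemoglobin change, transfusion, additional interventions and adverse events are recorded, with follow-up to discharge. An analysis plan not shown here may define the threshold windows.

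Most of this stands and limits the point. It does not remove it. The haemoglobin on the CRF (item 50) is the first value after control and may precede a later bleed. Transfusion and further treatment mark only bleeding serious enough to be treated. An analysis plan can define a window, but it cannot supply a volume that nobody collected.

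**Conclusion.** The point holds in a limited form. No volume is planned for bleeding that begins after tube removal, nor for comparable late loss in controls. Outcome 1 is an on-suction measure in the device arm, outcomes 2 and 3 have no window, and the caesarean checklist lacks the later reading that Procedures imply and the vaginal form provides.

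Whether this biases the comparison, and which way, cannot be determined from the documents. On the assumed range the shift in the mean difference runs from negligible (5 ml) to nearly the whole interval half-width (200 of 217 ml). Those figures place all late bleeding in the device arm and apply a caesarean SD throughout. They show what could go unseen and are not an estimate.

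This is a worthwhile, inexpensive improvement to secondary outcomes. It does not affect the primary outcome or the validity of the randomisation.

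**What to change.** - In both arms and both modes of birth, leave a tray or drape in place and take one cumulative reading at a common fixed time from delivery of the placenta, set after the tube is normally out. Two hours is one example. A clock running from the placenta also gives controls a start time, which insertion cannot.
- Define outcomes 2 and 3 on cumulative loss to that time.
- Keep the 30-minute volume as a separate outcome, labelled as early and on suction in the device arm.
- Reword CRF item 40 so that it is completed for every participant, covering loss from 30 minutes to the fixed time. Add the matching line to both checklists, including the caesarean form, which now has no such line for either arm.

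Cost: wording changes to the protocol, CRF and checklists, and about 40 + 40 = 80 extra readings with equipment already supplied. The tray stays in place longer and will collect some lochia, in both arms. Only measurement changes; when suction stops, when the tube is removed and how bleeding is treated are unaffected.

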Enrolment will take place immediately after birth of the baby when the participant's name is entered in the enrolment register and allocation takes place by opening the next in a consecutively numbered series of opaque sealed envelopes with allocation cards in computer-generated random sequence in balanced blocks of variable size, stratified by mode of birth. Participants will remain in the trial whether or not the intervention is applied, on the 'intention to treat' principle. Good Clinical Practice (GCP) procedures will be followed.

A clinical checklist will be completed by the attending clinician, which will form part of the patient clinical record. Data will be entered onto paper or electronic CRFs by the research staff.

Quality control will be performed on-site: the research staff will be responsible for ensuring that the CRFs are correctly filled out. Completed CRFs will be checked against the original patient records for correct completion. Any discrepancies will be immediately addressed.

Data management

Because of the small number of participants and limited data per participant, complex data entry strategies will not be needed. Data will be entered onto paper or electronic CRF's, checked for accuracy at source, and stored in a locked filing cabinet or password-protected computer. The data will be entered onto an excel spreadsheet and analysed using Epi Info software.

Adverse events and serious adverse events, whether thought to be related to the trial intervention or not, will be recorded by the site PIs on standard adverse events forms which will be submitted to the University ethics committee and DSMC.

Data protection procedures

The following measures will be taken to ensure participant confidentiality:

- Trial data sets for each participant will be identified by a unique ID number, not the participant's name
- The trial register of names and trial ID numbers, and consent forms will be kept separate from the CRFs
- Trial documents will be kept securely under lock and key and will not be accessible, other than to the research teams
- Data will be entered by trial ID number onto a password-protected database to which only trial staff will have access
- The trial report will not contain the names of any participants
- After completion of the trial, the trial documents will be kept under lock and key for five years

Personal information

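### The protocol gives two incompatible allocation moments: right after the baby is born (main text, caesarean checklist) and, at vaginal birth, only after the placenta and a trauma examination

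*Protocol*

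**What the plan says.** Under Quality assurance, During recruitment, the protocol ties register entry and allocation to one moment for every birth: "Enrolment will take place immediately after birth of the baby". Both the register entry and the opening of the next sealed envelope belong to that moment. Allocation is "stratified by mode of birth". The same paragraph adds: "Participants will remain in the trial whether or not the intervention is applied", on the intention-to-treat principle.

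The Caesarean birth Clinical checklist, item 6, reads: "After birth of baby, open next numbered envelope and note allocation". The time note (item 7) and the tube insertion (item 8) come afterwards, under a line that requires the "placenta delivered completely".

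The Vaginal birth Clinical checklist uses a different order. Item 6 positions the blood-collection tray once the baby is born. After the placenta comes item 7, "Examine vaginally to exclude major lower genital tract trauma", then a time note (item 8), and only at item 9 "Open next numbered envelope and note allocation". Insertion is item 10.

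Two other places depend on when enrolment happens. The Procedures section starts blood-loss measurement at enrolment. The Clinical Record Form marks treatment drugs (items 14 to 17) as given before enrolment and records additional drugs separately (items 32 to 35).

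**The concern.** At a vaginal birth the main text and the working form give different instructions about when a woman enters the trial. Between the two moments lie the delivery of the placenta and an examination, and either can show that the tube cannot be placed. Under the main text such a woman has already been allocated and stays in her arm. Under the checklist her envelope is still sealed at that point.

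Three things are at stake. The first is who is in the trial and how many device-arm women are actually exposed, when the Sample size section aims to use the device in 40. The second is the time origin of blood loss and of the before-enrolment drug record. The third, at caesarean, is an interval in an open-label trial during which the arm is known but the device cannot yet be in place.

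**Working it through.** The document gives no figure for this point, so the check compares the order of steps.

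| Step | Main text, all births | Caesarean checklist | Vaginal checklist |
|---|---|---|---|
| Baby born | Register entry and envelope | Envelope (item 6) | Tray positioned (item 6) |
| Placenta complete | not mentioned | Time noted (item 7) | heading before item 7 |
| Trauma examination | not mentioned | none | item 7 |
| Envelope | already opened | already opened | item 9 |
| Insertion | after allocation | item 8 | item 10 |

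1. *Number of moments.* There are two. The main text and the caesarean checklist share the first (after the baby, before the placenta). The vaginal checklist has the second (after the placenta and the examination). The direct contradiction is main text against vaginal checklist, for vaginal births.

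2. *How many women it covers.* The Sample size section asks for at least 25% vaginal and at least 25% caesarean births among 40 device-arm women. The minimum is 0.25 × 40 = 10 of either mode, so the maximum of the other is 40 − 10 = 30. The contradiction therefore covers 10 to 30 device-arm women, with similar numbers of controls under 1:1 allocation stratified by mode. The caesarean interval likewise concerns 10 to 30.

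3. *Exposure.* Each device-arm woman allocated but not treated removes 1/40 = 2.5 percentage points of exposure. The protocol gives no rate of failed or abandoned insertion, so no expected number can be derived from it.

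4. *Blood loss.* In the vaginal checklist the tray is in place at item 6 and is first replaced at item 21. If enrolment is at birth, the first tray reading starts at enrolment, as Procedures requires. If enrolment is at item 9, the same reading also holds blood lost before enrolment.

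5. *Drugs.* Take a drug given for bleeding after the birth but before the placenta is complete. By the main text it falls after enrolment and belongs with the additional drugs. By the vaginal checklist it falls before enrolment and belongs in items 14 to 17. Additional interventions to stop bleeding, including more uterotonics, are secondary outcome 10d, so the classification can change an outcome.

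6. *Eligibility.* The Inclusion Criteria do not mention the trauma examination. Because it stands before the envelope in the vaginal checklist, it could act as a screen there. It could not do so under the main text.

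**The case against.** The strongest reply is that little follows from the discrepancy. If one page is followed consistently, both arms of a stratum are allocated at the same point, so the randomised comparison is intact. Intention to treat retains women who do not receive the device, and both checklists provide for failed insertion, insertion not done and alternative management. The trial reports no p values, declares itself too small for a formal comparison, and has device effects and deficiencies as its primary outcome. Procedures are to be piloted before recruitment, which may bring the discrepancy to light. All of this stands and limits the severity. None of it tells staff which page to follow.

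One might also read the main text loosely, so that immediately after birth includes the third stage. That is hard to sustain: the caesarean checklist applies the phrase before the placenta, and the vaginal checklist itself separates the two stages.

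Several stronger readings are tempting, and the document does not support them:

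- *Three allocation moments.* Caesarean item 6 agrees with the main text, so there are two.
- *Women with major trauma are barred from randomisation.* No section says so. To exclude trauma can be ordinary diagnostic wording, and item 15 of the vaginal checklist expects repair of bleeding tears.
- *The caesarean surgeon knows the arm during the third stage.* This is likely: no blinding is described, and the attending clinician completes the checklist on which allocation is noted. But no section says who opens the envelope or who is told. The 15- and 30-minute checks run from placental delivery in both arms, and no size of bias can be shown.

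**Conclusion.** The concern holds as a contradiction between the recruitment section and the vaginal checklist, and it should be resolved before recruitment. It covers the 10 to 30 device-arm women expected to deliver vaginally and about as many controls. It leaves entry to the trial, the start of blood loss and the enrolment split of drugs dependent on the page followed.

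At caesarean the documents are consistent with each other. There the point is a weaker one of design: allocation is revealed earlier than insertion requires, in a trial without blinding.

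This is not a fatal flaw, and a reader should not infer that randomisation is compromised. The number of women allocated but untreated cannot be estimated from the protocol. Only the cost of each one (2.5 percentage points of 40) is known. The verdict assumes that the checklists are followed in their numbered order.

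**What to change.** Set one allocation point for both modes, as late as possible before insertion: register entry and envelope opening after complete delivery of the placenta and, at vaginal birth, after the examination already listed.

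- Amend the During recruitment paragraph to say so.
- Move caesarean item 6 below the line on complete delivery of the placenta.
- Tie the start of blood-loss measurement in Procedures, and the before-enrolment note on the Clinical Record Form, to that moment. State how blood already in the tray at a vaginal birth is to be handled.
- Have the sponsor state in the eligibility section whether the trauma examination is an eligibility check or only a clinical step.

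The cost is a few sentences and one moved checklist line. The downside is a brief pause before insertion at caesarean while the envelope is opened.
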